6.3 Concomitant Medications

6.3.1 General

All medications that were used from the time that written informed consent has been obtained through the SFU visit (at least 28 days [± 7 days] after the last dose of study drug) will be recorded in the eCRF. These are to include prescription and nonprescription medications, transfusions, vitamins, and nutritional supplements, and other remedies. Additional prior excluded medications are indicated in the Exclusion Criteria (Section 4.2).

6.3.2 Allowed Concomitant Medications

Standard supportive medications may be used in accordance with institutional guidelines and Investigator discretion. These may include hematopoietic growth factors to treat neutropenia, anemia or thrombocytopenia (in countries where hematopoietic growth factors are approved for use) in accordance with American Society for Clinical Oncology guidelines (but not for prophylaxis in C1); RBC and platelet transfusions, anti-emetic, analgesic and antidiarrheal medications; electrolyte repletion (e.g., calcium and magnesium) to correct low electrolyte levels; conditional use of steroids treatment as indicated in Section 6.3.3; thyroid replacement therapy for

hypothyroidism; and bisphosphonates, denosumab; and other medications for the treatment of osteoporosis, prevention of skeletal-related events from bone metastases, and /or hypoparathyroidism. Continuation of standard of care medications, including adjuvant hormonal therapy for patients with prostate cancer (e.g., gonadotropin-releasing hormone [GnRH] or luteinizing hormone-releasing hormone [LHRH] agonists) and breast cancer (e.g., GnRH/LHRH agonists, aromatase inhibitors, selective estrogen receptor modulators [SERMs] or degraders [SERDs]), that the patient has been on for the previous 28 days, are allowed, provided they are not on the list of prohibited concomitant medications (refer to Section 6.3.3 and Appendix D).

Local treatment while receiving selpercatinib (e.g., palliative radiation therapy or surgery for bone metastases) is permitted with Sponsor approval; however, the Sponsor recommends holding selpercatinib for approximately 5 half-lives (approximately 2 to 3 days) before and after radiation therapy or surgery. Any concern for disease flare due to a prolonged period off from selpercatinib should be discussed with the Sponsor, who may permit holding selpercatinib for a shorter period of time.

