1.6.2 Potential Drug Interactions

Selpercatinib has pH-dependent solubility and its PK can be affected by agents that modify gastric pH, such as proton pump inhibitors (PPIs) (e.g., omeprazole). Coadministration with multiple daily doses of omeprazole (PPI) decreased selpercatinib AUC_{0-INF} and C_{max} by 69% and 88%, respectively when selpercatinib was administered fasting. Coadministration with multiple daily doses of omeprazole did not significantly change the selpercatinib AUC_{0-INF} and C_{max} when selpercatinib was administered with food.

No clinically significant differences in selpercatinib PK were observed when coadministered with multiple daily doses of ranitidine (H₂ receptor antagonist) given 10 hours prior to and 2 hours after the selpercatinib dose (administered fasting). The effect of antacids that contain aluminum,

magnesium, calcium, simethicone, or buffered medicines on the PK of selpercatinib has not been specifically studied.

Coadministration of multiple doses of itraconazole (strong CYP3A inhibitor) increased the selpercatinib AUC_{0-1NF} by 133% and C_{max} by 30%; coadministration of multiple doses of diltiazem, fluconazole, or verapamil (moderate CYP3A inhibitors) is predicted to increase the selpercatinib AUC by 60 to 99% and C_{max} by 46 to 76%; coadministration of multiple doses of rifampin (strong CYP3A inducer) decreased the selpercatinib AUC_{0-1NF} by 87% and C_{max} by 70%; coadministration of multiple doses of bosentan or efavirenz (moderate CYP3A inducers) is predicted to decrease the selpercatinib AUC by 40 to 70% and C_{max} by 34 to 57%; coadministration of multiple doses of modafinil (weak CYP3A inducer) is predicted to decrease the selpercatinib AUC by 33% and C_{max} by 26%. Therefore, coadministration of selpercatinib with strong and moderate CYP3A inhibitors, strong and moderate CYP3A inducers, and CYP2C8 and CYP3A substrates should be avoided.

Coadministration of selpercatinib with repaglinide (sensitive CYP2C8 substrate) increased the repaglinide AUC_{0-1NF} by 188% and C_{max} by 91%. Avoid coadministration of selpercatinib with sensitive CYP2C8 substrates.

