Coadministration of selpercatinib with midazolam (sensitive CYP3A) increased the midazolam AUC_{0-1NF} by 54% and C_{max} by 39%. Therefore, selpercatinib can be considered a weak inhibitor of CYP3A4. Coadministration of selpercatinib with sensitive CYP3A4 substrates may increase their plasma concentrations, which may increase the incidence or severity of adverse reactions. Avoid coadministration of selpercatinib with sensitive CYP3A4 substrates.

Selpercatinib does not inhibit or induce CYP1A2, CYP2B6, CYP2C9, CYP2C19, or CYP2D6 at clinically relevant concentrations.

Selpercatinib inhibits MATE1, P-gp, and BCRP, but does not inhibit OAT1, OAT3, OCT1, OCT2, OATP1B1, OATP1B3, BSEP, and MATE2-K at clinically relevant concentrations. Selpercatinib may increase serum creatinine by decreasing renal tubular secretion of creatinine via inhibition of MATE1. Selpercatinib is a substrate for P-gp and BCRP, but not for OAT1, OAT3, OCT1, OCT2, OATP1B1, OATP1B3, MATE1, or MATE2-K. Selpercatinib may increase serum creatinine by decreasing renal tubular secretion of creatinine via inhibition of MATE1. Consider alternative markers of renal function if persistent elevations in serum creatinine are observed. The potential

for selpercatinib inhibition of P-gp or BCRP in the intestine cannot be ruled out. If coadministration of a sensitive P-gp or BCRP substrate cannot be avoided, patients should be monitored for increased adverse reactions of these drugs.

Additional details are provided in the selpercatinib IB.

2 Study Objectives

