6.3.3 Other Concomitant Medications

As selpercatinib is a substrate of CYP3A4, patients should avoid taking strong or moderate inhibitors or inducers of CYP3A4 as they could alter the drug's PK. If concomitant use of strong and moderate CYP3A inhibitors cannot be avoided, reduce the selpercatinib dosage and monitor the QT interval with ECGs more frequently.

Since selpercatinib is more soluble in an acidic environment than a neutral one, absorption may be impacted by stomach acidity, and concomitant use of pH altering agents require additional instructions. The concomitant use of PPIs should be avoided, and patients must take selpercatinib with food (at least 400 calories) when coadministered with a PPI if concomitant use cannot be avoided (refer to Appendix E).

When concurrent use of an H2 blocking agent is necessary, e.g., ranitidine (Zantac[®]), famotidine (Gaster[®]), or cimetidine (Tagamet[®]), it must be administered only 10 hours before or 2 hours after the dose of selpercatinib.

When concurrent use of an antacid is necessary, e.g., aluminum hydroxide/magnesium hydroxide/simethicone (Maalox[®]) or calcium carbonate (TUMS[®]), it must be administered 2 hours before and/or 2 hours after the dose of selpercatinib.

Chronic treatment (>7 days) with steroids is not permitted except to treat symptoms from an immune-related AE or brain metastases. Intermittent use of inhaled steroids for asthma or local steroid injections is allowed. Similarly, limited use of systemic corticosteroids (≤7 days) is permitted where it is considered SOC (e.g., as premedication for contrast allergy or for chronic obstructive pulmonary disease exacerbation). Replacement doses of steroids (e.g., prednisone 10 mg daily) are permitted while on study.

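### The concomitant-medication rules that sites are sent to (6.3.3 and Appendix D) omit the Section 1.6.2 instructions to avoid sensitive CYP2C8 and CYP3A4 substrates

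*Protocol*

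**What the plan says.** Protocol Section 6.3.2 covers standard-of-care medications that the patient has been on for the previous 28 days. They "are allowed, provided they are not on the list of prohibited concomitant medications (refer to Section 6.3.3 and Appendix D". The only examples given are hormonal therapies for prostate and breast cancer, introduced by the word 'including'.

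Protocol Section 1.6.2 contains these instructions on what selpercatinib does to other drugs:

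- CYP2C8: "Avoid coadministration of selpercatinib with sensitive CYP2C8 substrates". The supporting study is described as "Coadministration of selpercatinib with repaglinide (sensitive CYP2C8 substrate) increased the repaglinide" AUC by 188% and Cmax by 91%.
- CYP3A4: "Avoid coadministration of selpercatinib with sensitive CYP3A4 substrates". The supporting study is described as "Coadministration of selpercatinib with midazolam (sensitive CYP3A) increased the midazolam" AUC by 54% and Cmax by 39%, with the comment "Therefore, selpercatinib can be considered a weak inhibitor of CYP3A4".
- A broader sentence lists strong and moderate CYP3A inhibitors, then "strong and moderate CYP3A inducers, and CYP2C8 and CYP3A substrates should be avoided".
- For sensitive P-gp or BCRP substrates whose use is unavoidable, it asks for monitoring for adverse reactions to those drugs.

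Protocol Section 6.3.3 deals with the opposite direction, the effect of other drugs on selpercatinib: "patients should avoid taking strong or moderate inhibitors or inducers of CYP3A4 as they could alter the drug's PK". Appendix D tabulates CYP3A4 inhibitors, CYP3A4 inducers and QTc-prolonging agents.

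**The concern.** Section 6.3.2 makes permission depend on whether a drug is prohibited in 6.3.3 or Appendix D. If an avoid rule is missing from both, a drug in that class passes the test in 6.3.2 even though Section 1.6.2 says not to combine it with selpercatinib. The note to exclusion criterion 22 also sends sites to 6.3.2 for allowable concurrent therapies, so this is where a site would naturally look.

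What is at stake is the patient's exposure to the other drug. For sensitive CYP3A4 substrates, Section 1.6.2 itself says that raised concentrations may make adverse reactions more frequent or more severe.

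**Working it through.** No sample size, power or error rate is involved, so the check is a comparison of text plus a conversion of the protocol's percentages.

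**Step 1. Where each Section 1.6.2 rule reappears.**

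| Rule in 1.6.2 | In 6.3.3? | In Appendix D? |
|---|---|---|
| Avoid strong and moderate CYP3A inhibitors | Yes | Yes |
| Avoid strong and moderate CYP3A inducers | Yes | Yes |
| Avoid sensitive CYP2C8 substrates | No | No |
| Avoid sensitive CYP3A4 substrates | No | No |
| Monitor when sensitive P-gp/BCRP substrates are unavoidable | No | No |

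Of the two substrate avoid rules, 0 of 2 appear in 6.3.3 and 0 of 2 in Appendix D. In Appendix D the word 'substrate' occurs only in footnotes that grade inhibitor and inducer strength.

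**Step 2. Other places a site might look.** Section 6.3.1 points to the exclusion criteria for further excluded medications. Among criteria 19 to 36, the only class of non-cancer co-medication barred is QTc-prolonging drugs (criterion 34). Section 6.3.4 covers only hypersensitivity to the capsule components. Appendix E covers only proton pump inhibitors. None carries a substrate rule.

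**Step 3. Does it look deliberate?** The broader sentence in 1.6.2 names three groups together: CYP3A inhibitors, CYP3A inducers, and CYP2C8 and CYP3A substrates. The first two were carried into 6.3.3 and Appendix D and the third was not. The acid-reducer findings in 1.6.2 have matching instructions in 6.3.3. No reason is given for leaving substrates out, so omission is the likelier explanation.

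**Step 4. Size of the exposure change.** The inputs are the percentages in Section 1.6.2; fold change = 1 + percentage increase/100.

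- Repaglinide (CYP2C8) AUC: 1 + 1.88 = 2.88-fold. Cmax: 1 + 0.91 = 1.91-fold.
- Midazolam (CYP3A) AUC: 1 + 0.54 = 1.54-fold. Cmax: 1 + 0.39 = 1.39-fold.

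Midazolam serves here only as the protocol's example of the CYP3A class; it is not a likely drug to have been taken continuously for 28 days.

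**The case against.** The strongest reply is that the rule is in the protocol and is worded as an instruction. Section 1.6.2 applies to sites as much as 6.3.3 does, and each principal investigator signs after reading the protocol. This stands in part. A reader might infer that the protocol contradicts itself or positively authorises these substrates. The documents do not support that: 6.3.2 never mentions substrates, and 1.6.2 remains in force. What is shown is a missing carry-over and a missing cross-reference.

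Second, the examples in 6.3.2 are all hormonal therapies, so a drug such as repaglinide may lie outside what was meant. That is a genuine ambiguity. The word 'including' does not limit the permission to hormonal therapy, however, so a wider reading is open to a site.

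Third, Appendix D says its lists are not exhaustive and points to outside sources. That extends the inhibitor, inducer and QTc lists; it does not state a substrate rule. Similarly, sponsor approval under 6.3.3 is needed for exceptions to what that section sets out, and substrates are not set out there.

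Fourth, ongoing medications and those taken in the 14 days before the planned start are collected at screening, so a substrate would be on record before the first dose. This is a real opportunity to catch it, but the reviewer of that record still needs to know that the drug should be avoided.

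Finally, the CYP3A4 effect is weak and the frequency of such co-medication is unknown. Both stand, and both limit the size of the point.

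**Conclusion.** The gap is real and minor. It rests on two things: that a site decides on continued medications from 6.3.2 and the places it names, and that the 6.3.2 permission is read as extending beyond its hormonal examples. On that basis a site could continue a drug that 1.6.2 says to avoid. The weight falls on CYP2C8 (repaglinide AUC 2.88-fold); the CYP3A4 limb is much smaller.

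Two further inferences are tempting and unsupported. One is that many patients would be exposed: the documents give no co-medication frequency, so no count or rate can be claimed. The other is that the efficacy results are at risk. The interaction described raises levels of the other drug and is not described as altering selpercatinib exposure. No endpoint, population, sample size or analysis is affected.

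**What to change.** At the next protocol amendment, with a site memo in the meantime:

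1. In Section 6.3.3 and Appendix D, add an instruction to avoid sensitive CYP2C8 substrates (repaglinide as the example) and sensitive CYP3A4 substrates (midazolam as the example).
2. In Section 6.3.3, add the 1.6.2 advice on sensitive P-gp or BCRP substrates, as a monitoring instruction and not a prohibition.
3. In Section 6.3.2, add Section 1.6.2 to the cross-reference.

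Section 1.6.2 uses two scopes: one sentence covers CYP2C8 and CYP3A substrates generally, while the specific instructions say 'sensitive'. Whether to narrow the broader sentence is a safety decision for the sponsor and should not be made as an editorial alignment.

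This is a cheap improvement. It costs some wording and a memo, and some patients may need to switch a co-medication. Design, sample size and analysis stay as they are.

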6.3.3 Other Concomitant Medications

As selpercatinib is a substrate of CYP3A4, patients should avoid taking strong or moderate inhibitors or inducers of CYP3A4 as they could alter the drug's PK. If concomitant use of strong and moderate CYP3A inhibitors cannot be avoided, reduce the selpercatinib dosage and monitor the QT interval with ECGs more frequently.

Since selpercatinib is more soluble in an acidic environment than a neutral one, absorption may be impacted by stomach acidity, and concomitant use of pH altering agents require additional instructions. The concomitant use of PPIs should be avoided, and patients must take selpercatinib with food (at least 400 calories) when coadministered with a PPI if concomitant use cannot be avoided (refer to Appendix E).

When concurrent use of an H2 blocking agent is necessary, e.g., ranitidine (Zantac[®]), famotidine (Gaster[®]), or cimetidine (Tagamet[®]), it must be administered only 10 hours before or 2 hours after the dose of selpercatinib.

When concurrent use of an antacid is necessary, e.g., aluminum hydroxide/magnesium hydroxide/simethicone (Maalox[®]) or calcium carbonate (TUMS[®]), it must be administered 2 hours before and/or 2 hours after the dose of selpercatinib.

Chronic treatment (>7 days) with steroids is not permitted except to treat symptoms from an immune-related AE or brain metastases. Intermittent use of inhaled steroids for asthma or local steroid injections is allowed. Similarly, limited use of systemic corticosteroids (≤7 days) is permitted where it is considered SOC (e.g., as premedication for contrast allergy or for chronic obstructive pulmonary disease exacerbation). Replacement doses of steroids (e.g., prednisone 10 mg daily) are permitted while on study.

In addition, except as indicated in Section 6.3.2, patients are not allowed to receive concomitant systemic anti-cancer agents (including herbal products with anti-cancer activity), hematopoietic growth factors for prophylaxis in C1, therapeutic monoclonal antibodies, radiation therapy (palliative radiation therapy is permitted with Sponsor approval), drugs with immunosuppressant properties, or any other investigational agents besides selpercatinib. No new, alternative systemic anticancer therapy is allowed prior to documentation of PD in accordance with protocol-specified disease response criteria. If during the study, patients require initiation of treatment with strong inhibitors or inducers of CYP3A4 for clinical reasons, then the Sponsor should be consulted to determine whether selpercatinib should be stopped, and therefore whether the patient should be removed from the study. Strong and moderate inhibitors or inducers of CYP3A4 should be taken with caution. If concomitant use of strong and moderate CYP3A inhibitors cannot be avoided, reduce the selpercatinib dosage and monitor the QT interval with ECGs more frequently. Any exceptions to the above must be approved by the Sponsor.

6.3.4 Contraindications

Selpercatinib is contraindicated in patients with known hypersensitivity to any of its capsule components.

6.4 Discontinuation of Study Intervention

Patients will be advised that they are free to discontinue study treatment at any time and that they will be followed for survival after discontinuing treatment (refer to Section 7.6). Over the course of the study, the Investigator and/or the Sponsor should remove a patient from treatment for any of the reasons listed below:

- PD
Exception: Patients with documented PD who are tolerating treatment and, in the opinion of the Investigator, are deriving clinical benefit from continuing study treatment, may continue treatment with prior Sponsor approval.
- Unacceptable toxicity
- Intercurrent illness compromising ability to fulfill protocol requirements
- Pregnancy
- Requirement for alternative treatment in the opinion of the Investigator, unless such treatment is temporary (e.g., local radiation or surgery for disease that does not meet the definition of PD)
- Significant noncompliance with protocol
- Withdrawal of consent by the patient
- Lost to follow-up
- Death
- Study terminated by Sponsor

Participants discontinuing from the investigational product for any reason should complete adverse event per Table 7-1 (Schedule of Activities), Section 8.2 (Safety Assessments) of the protocol.

At the time a patient discontinues treatment, all safety data normally required at the EOT visit will be obtained if possible, as outlined in Section 7.4. Patients will enter LTFU where they may be required to undergo disease assessments (refer to Section 7.6).

6.4.1 Discontinuation of Inadvertently Enrolled Patients

If Lilly or the investigator identifies a patient who did not meet enrollment criteria and was inadvertently enrolled, a discussion must occur between the Lilly CRP and the investigator to determine if the patient may continue in the study. If both agree it is medically appropriate to continue, the investigator must obtain documented approval from the Lilly CRP to allow the inadvertently enrolled patient to continue in the study with or without study drug. Patients who are discontinued from study drug will have follow-up procedures performed as shown in the Schedule of Activities (Table 7-1).

6.5 Discontinuation/ Withdraw from the Study

Discontinuation from the Study and reasons for end of study could be:

- Withdrawal of consent by the patient
- Lost to follow up
- Death
- Study terminated by Sponsor

Patients who are discontinued from the study will have follow-up procedures performed as shown in the Schedule of Activities.

6.6 Lost to Follow-Up

A patient will be considered lost to follow-up if he or she repeatedly fails to return for scheduled visits and is unable to be contacted by the study site. Study site personnel are expected to make diligent attempts to contact patients who fail to return for a scheduled visit or who the site is otherwise unable to follow-up.

Study site personnel, or an independent third party, will attempt to collect the survival status for all enrolled patients who are lost to follow-up, including enrolled patients who do not receive study drug, within legal and ethical boundaries. Public sources may be searched for survival status information. If the patient's survival status is determined, the survival status will be documented, and the patient will not be considered lost to follow-up.

Lilly personnel will not be involved in any attempts to collect survival status information.

7 Tests and Evaluations

All required observations and their schedules are summarized in [Table 7-1](#) and are described in more detail in the following subsections.

RET alternation from Cohort 1 and 2 will be confirmed centrally. Special assessments, such as PK, will be performed centrally. Additional information regarding handling and processing of these special samples is provided in the separate Laboratory Manual.

Routine laboratories, for example serum chemistries, hematology, and urinalysis, will be performed locally. For each thyroid cancer patient, tests for calcitonin and CEA (MTC patients) and thyroglobulin (non-MTC thyroid cancer patients) should be performed in the same laboratory to minimize intra-patient, lab-to-lab variability in their measurement.

Unless otherwise noted, the routine laboratories and procedures will be performed prior to dosing as noted, and routine evaluations performed within -2 days of the visit day will not be considered protocol deviations.

During the conduct of this study, the Sponsor must be notified of the collection of samples outside of this protocol for separate institutional investigations.

Table 7-1 Schedule of Activity (SoA)

| Visit Window | Screening | Cycle 1 | | | | Cycle 2-higher | SFU ^b | | LTFU ^c |
|---|-----------------------------------|----------------|----------------|----------------|-----------------------------|----------------------------|------------------------------|-----------------|-------------------|
| | Up to 28 days prior to first dose | D1 ±2 Days | D8 ±2 Days | D15 ±2 Days | D22 ^d ±2 Days | ±2 Days | EOT ^a ≤ 7 days | D 28 ±7 days | |
| Informed Consent ^e | X | | | | | | | | |
| Inclusion/exclusion criteria | X | | | | | | | | |
| Medical, surgical, malignancy history | X | | | | | | | | |
| Molecular Pathology Report(s) describing RET and other alterations ^f | X | | | | | | | | |
| Archived tumor tissue or fresh biopsy ^g | X | | | | | | | | |
| Physical examination and ECOG ^h | X | X | X | X | | D1 C2, 3, 4, 5, etc. | X | X | |
| Vital signs ⁱ | X | X ^j | X ^j | X ^j | | D1 C2, 3, 4, 5, etc. | X | X | |
| 12-lead ECG ^k | X | X | X | | | D1 C2-6 and every 12 weeks | X | X ^l | |
| Urine or serum pregnancy test ^m | X | X | | | | D1 C2, 3, 4, 5, etc. | | | |
| Hematology ⁿ | X | X | X | X | | D1 C2, 3, 4, 5, etc. | X | X | |
| Serum chemistries ^o | X | X | X | X | | D1 C2, 3, 4, 5, etc. | X | X | |
| Liver function tests ^p | | | | | | C2D15 and C3D15 | | | |

| Visit Window | Screening | Cycle 1 | | | | Cycle 2-higher | SFU ^b | | LTFU ^c |
|--|-----------------------------------|---------------|---------------|----------------|-----------------------------|--|------------------------------|-----------------|-------------------|
| | Up to 28 days prior to first dose | D1 ±2 Days | D8 ±2 Days | D15 ±2 Days | D22 ^d ±2 Days | ±2 Days | EOT ^a ≤ 7 days | D 28 ±7 days | |
| Coagulation ^q | X | X | | | | | | | |
| Thyroid panel ^t | X | | | X | | D1 of odd cycles beginning with C3 (C3, 5, 7, etc.) | | | |
| Urinalysis ^s | X | | | X | | D1 C2, and as clinically indicated. | X | X | |
| Calcitonin, CEA (MTC only) ^t | X | X | | X | | D1 C2 and odd-numbered cycles, starting with C3 through C13. Every 12 weeks thereafter (±7 days of each radiologic disease assessment) | X | | |
| Thyroglobulin (non-MTC thyroid cancers only) ^u | X | X | | X | | D1 C2 and odd-numbered cycles, starting with C3 through C13. Every 12 weeks thereafter (±7 days of each radiologic disease assessment) | X | | |
| Blood cortisol, ACTH, 24-hour urine for free cortisol ^v | X | X | | X | | D1 C2 and odd-numbered cycles, starting with C3 through C13. Every 12 weeks thereafter (±7 days of each radiologic disease assessment) | X | | |
| Disease assessment ^w | X | | | | | Perform assessments at week 4 (±7 days, optional) and week 8 (±7 days) and then every 8 weeks (±7 days) until week 48 following C1D1 and then every 12 weeks (±7 days) | X ^x | | X ^y |
| Confirmatory disease assessment ^z | | | | | | At least 4 weeks post 1 st PR | | | |
| Blood sample for intensive PK ^{aa} | | X | X | | | | | | |
| Blood sample for PopPK ^{bb} | | X | | | | D1 of each cycle Predose sample to be drawn | | | |
| EORTC QLQ-C30 ^{cc} | | X | | | | Every 8 weeks (±7 days) starting with D1 C3 through D1 C13. Every 12 weeks (±7 days) thereafter | X | | |

| Visit Window | Screening | Cycle 1 | | | | Cycle 2-higher | SFU ^b | | LTFU ^c |
|--|-----------------------------------|---------------|---------------|----------------|-----------------------------|----------------------|------------------------------|-----------------|-------------------|
| | Up to 28 days prior to first dose | D1 ±2 Days | D8 ±2 Days | D15 ±2 Days | D22 ^d ±2 Days | ±2 Days | EOT ^a ≤ 7 days | D 28 ±7 days | |
| Dispense selpercatinib | | X | | | | D1 of each cycle | | | |
| Selpercatinib administration | | | | | | | | | |
| Patient dosing diary | | | | | | | | | |
| Patient bowel diary (MTC only) ^{dd} | | X | X | X | X | D1 C2, 3, 4, 5, etc. | X | | |
| Adverse events ^{ee} | | | | | | | | | |
| Concomitant medications ^{ff} | | | | | | | | | |
| Survival ^{gg} | | | | | | | | X | X |

Abbreviations (for Table 7-1 and Footnotes): ACTH-adrenocorticotrophic hormone; AE-adverse event; ALP-alkaline phosphatase; ALT-alanine aminotransferase; AST-aspartate aminotransferase; BUN blood urea nitrogen; C-cycle; CEA carcinoembryonic antigen; CR complete response; CT-computed tomography; D-day; ECG electrocardiogram; ECOG-Eastern Cooperative Oncology Group; EORTC QLQ-C30-European Organization for Research and Treatment of Cancer Quality of Life Questionnaire-Core 30; EOT-End of Treatment; IV intravenous; LDH lactate dehydrogenase; LTFU long-term follow up; MTC medullary thyroid cancer; MRI magnetic resonance imaging; PD-progressive disease; PK pharmacokinetics; PR partial response; RBC-red blood cell; SAE-serious adverse event; SFU safety follow-up; TSH-thyroid-stimulating hormone; T3-free triiodothyronine; T4-free thyroxine; WBC white blood cell.

- End of Treatment (EOT): +7 days of the last dose or the decision to terminate treatment. If lab testing is performed ≤7 days prior to EOT, repeat testing does not need to occur on EOT.
- Safety Follow-Up (SFU): 28 days (±7 days) after last dose of study drug.
- Long-Term Follow-Up (LTFU): approximately every 3 months (±1 month) for up to two years after the last dose of study drug.
- Telephone contact for safety.
- Patient must re consent prior to continuing to receive study treatment beyond progression.
- For all patients, redacted report(s) to be submitted to Sponsor or designee during Screening /prior to enrollment.
- Adequate availability of archived tumor tissue should be confirmed, either tumor block (preferred) or ~10 × 5µm unstained slides should be provided. Patients who do not have sufficient archival tumor tissue available should undergo an optional fresh tumor biopsy, if it is considered safe to perform, prior to

treatment. If sufficient archived tumor tissue is not available and a fresh biopsy cannot be safely performed, the patient may still be eligible with prior Sponsor approval.

- h. Physical examination of and review of relevant systems at Screening, body weight, and height. Symptom-directed physical examinations, including measurement of weight may be performed at other time points.
- i. Systolic and diastolic blood pressure, heart rate, respiratory rate, and body temperature.
- j. Vital signs should be conducted as follows:
 - C1D1, C1D8: pre-dose (up to 4 hours pre-dose, as close to dosing as possible is preferred) and post-dose at 2 hours (± 30 minutes). Vital signs should be performed prior to collection of PK blood sample drawn at that time point.
 - C1D15, Day 1 of C2-higher: pre-dose (up to 4 hours pre-dose, as close to dosing as possible is preferred);
- k. Obtain a single pre-dose ECG during Screening and again on C1D1. If the C1D1 pre-dose QTcF > 470 msec (QTcF = QT (msec)/RR^{1/3}), where RR (msec) = $60 \times 1000/\text{BPM}$), the Sponsor should be notified prior to dosing to determine whether the patient remains eligible. On C1D8, C2D1 and thereafter, perform a single ECG at 2 hours (± 10 minutes) post-selpercatinib dosing. On C1D8 PK collection, an extra ECG should be timed prior to the PK sample being drawn. Dose patients in the visit to ensure accuracy of timing. If any ECG demonstrates QTcF 481-500 msec, perform an additional ECG at the same day, specific time judged by investigator. If any ECG demonstrates QTcF > 500 msec, repeat the ECG twice (triplicate in total) at the same day, specific time judged by investigator, and manually review to confirm accuracy. If QTcF > 500 msec is confirmed on 2/3 ECGs, hold selpercatinib and assess for alternative causes (concomitant medications, electrolyte abnormalities). Potassium should be > 4 mEq/L and $< \text{ULN}$ and magnesium and calcium should be within normal limits. selpercatinib may be resumed at one reduced dose level when QTcF has returned to baseline value, and with continued ECG monitoring as noted in the assessment schedule.
- l. Repeat only if EOT reading showed treatment-emergent abnormalities.
- m. For women of childbearing potential: Serum pregnancy test at Screening, serum or urine pregnancy test at Day 1 of every cycle (-2 days) (surgically sterilized females or those who have not experienced menses for at least 2 years are not required to be tested i.e., post-menopausal women who have not had menses within the last 12 months but have had menses within the last 24 months will be required to have a serum pregnancy test performed.). If screening testing is performed ≤ 7 days prior to C1D1, repeat testing does not need to occur on C1D1.
- n. Hemoglobin, hematocrit, RBC count, WBC count with differential (neutrophils [count and percent] and lymphocytes, monocytes, eosinophils, basophils [percent]), and platelet count). Patients found to have treatment-emergent hematologic toxicity of Grades 3 or 4 will be monitored at least weekly until resolution. If screening testing is performed ≤ 7 days prior to C1D1, repeat testing does not need to occur on C1D1.
- o. Detailed serum chemistries (non-fasting) please see [appendix H](#). Note number: ≤ 14 days before pre-dose on screening period. If screening testing is performed ≤ 7 days prior to C1D1, repeat testing does not need to occur on C1D1. Patients found to have treatment-emergent laboratory toxicity of Grades 3 or 4 will be monitored at least weekly until resolution.
- p. Collect AST, ALT, ALP, and total and direct bilirubin on C2D15 and C3D15 (± 2 days).
- q. Additional assessments may be obtained at the discretion of the investigator. If screening testing is performed ≤ 7 days prior to C1D1, repeat testing does not need to occur on C1D1.
- r. If screening testing is performed ≤ 7 days prior to C1D1, repeat testing does not need to occur on C1D1. Thyroid-stimulating hormone (TSH), free triiodothyronine (FT3), and free thyroxine (FT4).
- s. If screening testing is performed ≤ 7 days prior to C1D1, repeat testing does not need to occur on C1D1. Detailed urinalysis please see [appendix H](#).

- t. If screening testing is performed ≤ 7 days prior to C1D1, repeat testing does not need to occur on C1D1. Calcitonin and CEA only for patients with a diagnosis of MTC. These should be performed in the same laboratory to minimize intra-patient, lab-to-lab variability in their measurement.
- u. If screening testing is performed ≤ 7 days prior to C1D1, repeat testing does not need to occur on C1D1. Thyroglobulin only for patients with non-MTC thyroid cancers (unless not measurable due to the presence of anti-thyroglobulin antibodies). These should be performed in the same laboratory to minimize intra-patient, lab-to-lab variability in their measurement.
- v. If screening testing is performed ≤ 7 days prior to C1D1, repeat testing does not need to occur on C1D1. Optional for MTC or other cancer patients with Cushing's disease related to their cancer. If performed, urine collection should begin pre-dose. If blood cortisol, ACTH cannot be measured locally, central laboratory will be used to perform the test.
- w. Baseline disease assessment with radiographic tumor measurements using CT or MRI of chest, abdomen, and pelvis; And any other areas with suspected disease involvement within 28 days of C1D1 as clinically indicated. Brain imaging is required at baseline for all RET fusion-positive patients, patients with a history of CNS metastases, or other patients if clinically indicated and subsequent serial scans if brain metastases are present at baseline (MRI preferred, CT with contrast is acceptable if MRI contraindicated). Required only for patients with nonmeasurable bone disease identified at baseline or if clinically indicated. For each modality, IV and oral contrast should be utilized unless there is a clear contraindication (e.g., decreased renal function or allergy that cannot be addressed with standard prophylactic treatments). In the absence of known or suspected disease involvement, head and neck CT/MRI scans are not required for malignancies other than those originating in the head and neck region. Other areas of scanning may also differ depending on disease type. Post-baseline scans should be performed every 8 weeks (± 7 days) until week 48 and every 12 weeks (± 7 days) thereafter, including imaging of the chest, abdomen, and pelvis, using the same modality(ies) as used for baseline imaging assessment until PD, withdrawal of consent, or initiation of a new anticancer therapy(ies). Additionally, any studies performed at baseline that are positive for sites of disease should be repeated at all post-baseline assessments. Additional studies can also be performed as clinically indicated. In addition, Investigators may conduct an initial tumor evaluation on week 4 (± 7 days) and a confirmatory tumor evaluation a minimum of 4 weeks (i.e., 28 days) after the first tumor evaluation that shows a CR or PR by RECIST 1.1, if consistent with local regulatory authority requirements. In addition, an initial post baseline assessment on week 4 (± 7 days) is encouraged if consistent with regulatory guidelines. If a scan is performed on week 4, the next scan should continue according to the schedule above (beginning at week 8). For patients who continue to receive study treatment beyond progression, post PD scans to determine tumor disease assessment should be performed within 8 weeks (± 7 days) of initial PD (PD₁) and every 8 weeks (± 7 days) thereafter until subsequent PD (PD₂), withdrawal of consent, or initiation of a new anticancer therapy(ies). Additional scans can be performed as needed. All scans (including any unscheduled scans performed during the study) will be collected and stored at a central facility to permit central reviewer assessment. Please see the Site Imaging Manual for guidelines on how the various imaging studies should be performed.
- x. If not performed within the last 8 weeks.
- y. Patients who discontinue study drug for reasons other than PD (e.g., AE, noncompliance, etc.) may (but for practical reasons and to minimize patient inconvenience, are not required to) undergo additional disease assessment by imaging (as specified above until PD, withdrawal of consent or initiation of a new anticancer therapy(ies)).
- z. Confirmatory scans: Minimum of 4 weeks (e.g., 28 days) after the first tumor evaluation showing a CR or PR by RECIST 1.1, if permitted by regulatory authorities. The next scan should continue according to the schedule above.
- aa. For 12 subjects in intensive PK testing, PK test performed on C1D1: Up to pre-dose, and post-dose 1 hour (± 15 minutes), 2 hours (± 15 minutes), and 4 hours (± 15 minutes), 8 hours (± 30 minutes) and 12 hours (± 30 minutes), C1D8: Up to pre-dose, and post-dose 1 hour (± 15 minutes), 2 hours (± 15 minutes), and 4 hours (± 15 minutes) and 8 hours (± 30 minutes).
- bb. For all enrolled subjects in PopPK testing, PK test performed on each cycle D1 predose.

- cc. EORTC QLQ-C30. The questionnaires should be answered by the subject to the best of his/her ability, prior to receiving drug on C1D1 and preferably prior to learning the results of the radiologic disease assessment for subsequent cycles.
- dd. Only for patients with a diagnosis of MTC and diarrhea at baseline. Two patient bowel diary cards will be dispensed on C1D15. The questionnaires should be answered by the subject to the best of his/her ability.
- ee. AEs and SAEs should be recorded from the time that written informed consent has been obtained through the SFU Visit.
- ff. Concomitant, ongoing medication(s) plus those administered within 14 days prior to the planned start of treatment.
- gg. Patients will be followed for survival status, date of progression, and subsequent anticancer therapy(ies) by telephone or other method.

